#### **Estimated Duration of Participation:**

**Screening:** Up to 28 days.

**Baseline:** 7 days before first dose of INCB050465.

**Treatment:** Begins with the first dose of INCB050465 (Day 1). Treatment will continue as long as the regimen is tolerated and the subject does not meet discontinuation criteria. Subjects who discontinue study treatment will be followed for subsequent MF treatments and survival.

**Follow-up:** 30 to 35 days after the last dose of medication is taken.

**Survival follow-up:** Until subject dies.

It is estimated that an individual subject will participate for approximately 24 months.

**Principal Coordinating Investigator:** [REDACTED], MD, MD Anderson Cancer Center, Houston, TX

#### **Statistical Methods:**

The primary endpoint of change from baseline in spleen volume at Week 12 will be compared between subjects randomized to TG5D and TG5I/M + TG5 in Parts 3 and 4 of the study using a van Elteren test to account for stratification by ECOG performance status at screening (ECOG 0-1 vs 2). If either of the 2 ECOG-based stratum in Part 4 fail to enroll a sufficient number of subjects, the primary endpoint will be assessed using a 2-sample Wilcoxon rank sum test with a normal approximation to the test statistic.

Results for subjects enrolled to TG10 and TG20 will be summarized descriptively with no formal statistical comparisons performed. The MTD was determined during the Part 1 safety run-in portion of the study based on the proportions of subjects experiencing DLTs. Adverse events will be tabulated for all parts of the study.

According to the Wilcoxon rank sum test, the primary efficacy endpoint has a 90% probability to reject the null hypothesis if the 2 treatment groups differ in percentage change in spleen volume from baseline at Week 12 by 11.4 percentage points with 30 subjects per treatment group, assuming both treatment groups are normally distributed with standard deviation of 14.5.

Secondary efficacy analyses will be conducted for the intent-to-treat population. Change and percentage change from baseline in quantitative variables will be summarized using descriptive statistics. Results for subjects enrolled to TG10 and TG20 will be compared descriptively to those of the other treatment groups, but no direct statistical comparisons are planned.

A difference between TG5D and TG5I/M + TG5 in total symptom score evaluated by the MFSAF v3.0 symptom diary and the MPN-SAF will be assessed separately using a van Elteren test to account for stratification by ECOG performance status. If TG5D or TG5I/M + TG5 in the randomized portion of the study fail to enroll a sufficient number of subjects in a particular stratum, then the difference in the 2 treatment groups for these endpoints will be assessed separately using a 2-sample Wilcoxon rank sum test with a normal approximation applied to the test statistic.

All other efficacy endpoints are exploratory in nature and will be tabulated by summary statistics.

There will be 1 planned interim analysis conducted for futility for this study. The interim analysis will be conducted during the randomized portion of the study once TG5D and TG5I/M + TG5 enroll 15 subjects and have been evaluated for spleen volume at Week 12. Further enrollment in a treatment group will be terminated if fewer than 4 subjects in the treatment group have spleen stability or a reduction from baseline in spleen volume (ie, percentage change from baseline  $\leq 0\%$ ) as measured by MRI (or CT scan in applicable subjects) at Week 12. Subjects remaining in any terminated group may have their dose adjusted to reflect the ongoing group with sponsor approval.

If either TG5D or TG5I/M is terminated, then Part 4 will continue as a single-group study, and the primary endpoint will be analyzed. If both TG5D and TG5I/M are terminated, then the study will be terminated. The probabilities of stopping a treatment group for futility for various probabilities of a subject achieving  $\geq 0\%$  decrease from baseline in spleen volume at Week 12 are provided in the full body of the Protocol.

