### **7.6.3. Imaging**

The primary measure of spleen size will be by MRI (or CT scan in applicable subjects). An MRI of the upper and lower abdomen and pelvis will be performed at baseline, Week 12 and Week 24, and every 12 weeks thereafter through Week 108. An MRI will be performed with a body coil because the objective is to measure organ volume, not to find very small lesions. The MRIs will be read initially by local radiologists who will assess the scan for quality and send all scans (MRI or CT) to the central imaging laboratory the same day, if at all possible. The scans from an individual subject will be read by a central reader. Spleen and liver volume will be obtained by outlining the circumference of the organ and determining the volume using the validated technique of least squares. The MRI will not determine spleen length below the costal margin, as there are no validated approaches for determining this measurement. Procedure-specific training for scanning and image capture will be provided by the vendor.

An MRI is the preferred method for obtaining spleen volume data. However, CT scans may be performed at the visits where MRI is designated if the subject is not a candidate for MRI (eg, because of the presence of metal clips in the body, because of claustrophobia) or if MRI is not readily available. CT scans will be similarly processed by the same central laboratory as used for MRIs. Procedure-specific training for scanning and image capture will be provided by the vendor. NOTE: The same method (MRI vs CT) must be used for all visits for a given subject unless a new contraindication to the use of MRI occurs (eg, pacemaker insertion).

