### 9.5.2. Interim Efficacy Analysis

There will be 1 planned interim analysis conducted for futility for this study. The interim analysis will be conducted during the randomized portion of the study once TG5D and TG5I/M + TG5 enroll 15 subjects and have been evaluated for spleen volume at Week 12. Further enrollment in a treatment group will be terminated if fewer than 4 subjects in the treatment group have spleen stability or a reduction from baseline in spleen volume (ie, percentage change from baseline  $\leq 0\%$ ) as measured by MRI (or CT scan in applicable subjects) at Week 12. Subjects remaining in any terminated group may have their dose adjusted to reflect the ongoing group with sponsor approval.

If either TG5D or TG5I/M is terminated, then Part 4 will continue as a single-group study, and the primary endpoint will be analyzed as described in Section 9.4.1.4. If both of the treatment groups are terminated, then the study will be terminated. The probabilities of stopping a treatment group for futility for various probabilities of a subject achieving  $\geq 0\%$  decrease in spleen volume at Week 12 are provided in Table 16.

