**Table 16: Probability of Stopping a Treatment Group for Futility**

Probability of Subject Having $\geq 0\%$ Decrease in Spleen Volume at Week 12 in a Treatment Group	Probability of Stopping a Treatment Group for Futility
5%	99.5%
10%	94.4%
20%	64.8%
25%	46.1%
30%	29.7%
40%	9.1%
50%	1.8%

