9. INTERIM ANALYSES

There will be no planned, formal interim analyses for the Part 1 dose escalation portion of the study. The review of accrued clinical data will be conducted by Incyte and provided to study investigators via teleconferences at the end of Part 1 of the study. Based on review of the most current safety data, the sponsor (in consultation with the study investigators and using the dose-escalation/de-escalation rules) will determine if and at what dose additional participants should be treated in the study.

For TG5D and TG5 (TG5I/M) in the safety population, a formal interim analysis for futility is planned after 15 participants are enrolled into each treatment group and have discontinued or had their Week 12 visit. If 4 or fewer participants in a given dose group have spleen stability or a reduction from baseline in spleen volume (ie, percentage change from baseline $\leq 0\%$) as measured by MRI (or CT scan in applicable participants), then the dose in question will be terminated.

If either TG5D or TG5 (TG5I/M) is terminated, then Part 4 will continue as a single-arm study, and the primary endpoint will be analyzed as described in Section 3.6. If both of the treatment groups are terminated, the study will be terminated. The probabilities of stopping a treatment group for futility for various probabilities of a participant achieving $\geq 0\%$ decrease in spleen volume at Week 12 are provided in [Table 8](#). Additional operational details of the interim analyses, including TFLs provided to the DMC, will be provided in the DMC Charter.

Table 8: Probability of Stopping a Treatment Group for Futility

Probability of Participant Having $\geq 0\%$ Decrease in Spleen Volume at Week 12 in a Treatment Group	Probability of Stopping a Treatment Group for Futility
5%	99.5%
10%	94.4%
20%	64.8%
25%	46.1%
30%	29.7%
40%	9.1%
50%	1.8%

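### The Protocol and the SAP fill the 15 places of the futility look differently, and neither ties the success count to the first 15

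*Protocol*

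**What the plan says.** **When the look happens.** The Protocol Synopsis (Statistical Methods) and Protocol Section 9.5.2 use the same words: the look takes place "once TG5D and TG5I/M + TG5 enroll 15 subjects and have been evaluated for spleen volume at Week 12". SAP Section 9 places it "after 15 participants are enrolled into each treatment group and have discontinued or had their Week 12 visit". SAP Section 10.1, the place to record departures from Protocol-defined analyses, is marked not applicable.

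**What triggers a stop.** Protocol Section 9.5.2: "Further enrollment in a treatment group will be terminated if fewer than 4 subjects in the treatment group have spleen stability" or a reduction. SAP Section 9: "If 4 or fewer participants in a given dose group have spleen stability or a reduction from baseline in spleen volume". Both define success by an imaging result; the Protocol's words are "as measured by MRI (or CT scan in applicable subjects) at Week 12". Neither says how to score a participant who has no Week 12 scan, and neither confines the count of successes to the 15 who triggered the look.

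**When scans are taken.** Under Protocol Section 7.6.3, MRI "will be performed at baseline, Week 12 and Week 24, and every 12 weeks thereafter through Week 108". No scan is listed for the end-of-treatment visit.

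**The printed probabilities.** Protocol Table 16 ("Probability of Stopping a Treatment Group for Futility") and SAP "Table 8: Probability of Stopping a Treatment Group for Futility" carry the same seven rows. The left column is headed as a per-subject probability within a treatment group. It does not say whether that means subjects with a scan or all subjects counted.

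**The primary analysis.** Protocol Section 9.4.1.1 and SAP Section 7.3.1 give the worst rank in the stratum to anyone who discontinues or lacks a Week 12 volume. That rule is written for the primary test and not for the interim look.

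**The concern.** The look can close a group, and closes the study if both groups fail, so it should be clear who is counted. Under the SAP, a participant who stops before Week 12 helps complete the 15. With no scan, that participant cannot be a success. Under the Protocol's literal wording, the same participant has not been evaluated at Week 12 and the 15 are not yet complete. The two documents can therefore call the look at different times and on different people.

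Two further gaps affect how the table is read. Both rules count successes in the group as a whole. If one group has more than 15 evaluated when the other reaches 15, the fixed cut-off is applied to a larger number and stopping becomes less likely than printed. The success rate in the left column is also undefined. A reader who takes it as the rate among scanned subjects will understate the stopping risk wherever discontinuers are counted.

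**Working it through.** **Inputs.** n = 15 per group (both documents). Stop at 3 or fewer successes (Protocol) or at 4 or fewer (SAP). The documents give no rate of discontinuation before Week 12, so d = 10% to 20% is assumed for illustration.

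**Step 1: reproduce the printed table.** P(stop) = P(X ≤ 3), X ~ Binomial(15, p).

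| p | Printed (both tables) | P(X ≤ 3), n = 15 | P(X ≤ 4), n = 15 |
|---|---|---|---|
| 5% | 99.5% | 99.45% | 99.94% |
| 10% | 94.4% | 94.44% | 98.73% |
| 20% | 64.8% | 64.82% | 83.58% |
| 25% | 46.1% | 46.13% | 68.65% |
| 30% | 29.7% | 29.69% | 51.55% |
| 40% | 9.1% | 9.05% | 21.73% |
| 50% | 1.8% | 1.76% | 5.92% |

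All seven rows match 15 counted subjects and the Protocol's cut-off. They do not describe the SAP's own cut-off: at p = 40% that rule gives 21.7% against the printed 9.1%, before any discontinuation.

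**Step 2: count discontinuers as non-successes.** Let p be the success rate among scanned participants. The rate per counted participant is p(1 − d), with n still 15. At the Protocol's cut-off:

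| p among scanned | d = 0 | d = 10% | d = 20% |
|---|---|---|---|
| 30% | 29.7% | 39.1% (rate 0.27) | 49.8% (rate 0.24) |
| 40% | 9.1% | 15.3% (rate 0.36) | 24.2% (rate 0.32) |
| 50% | 1.8% | 4.2% (rate 0.45) | 9.1% (rate 0.40) |

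This is the same binomial function at a lower rate. For example, p = 50% with d = 20% gives a rate of 0.40 and returns the table's own 40% row.

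These figures isolate the effect of the counted set. With the SAP's cut-off as well, the p = 40% row becomes 21.7%, 32.2% and 44.8%.

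**Step 3: more than 15 evaluated.** With the cut-off fixed at 3 or fewer and p = 20%, P(stop) is 64.8% at n = 15, 59.8% at n = 16 and 41.1% at n = 20.

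**Step 4: a case.** Fifteen are enrolled in a group, 3 stop early, 12 are scanned and 3 of those are at or below 0%. Under the SAP the 15 places are filled, with 3 successes. Under the Protocol's literal wording 12 have been evaluated and the look is not due. Later scans could leave the count at 3 or raise it.

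**The case against.** The Protocol sentence is a timing trigger and never mentions discontinuers, so their exclusion is an inference. The stopping rule itself counts measured successes, and an unscanned subject adds none under either document. Protocol Section 9.4 leaves the full description of analyses to the SAP, so the SAP wording can be read as supplying the detail. SAP Section 5.3.2 treats someone who discontinued treatment by the visit as evaluable for spleen volume, and the primary analysis gives missing values the worst rank; both point the same way. SAP Section 9 also defers operational detail to a DMC Charter that is not available here. Finally, allocation seems designed to bring both groups to 15 together: 3:2 for the first 25 in Part 4 gives 15 and 10, and the roughly 5 Part 3 subjects would make up the difference if they are in TG5.

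Much of this stands, and it rules out some stronger readings that a reader might infer:

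- *That the Protocol excludes discontinuers by rule, contradicting the primary analysis.* It is silent. Protocol Section 5.6.2 also allows some subjects to continue efficacy follow-up after stopping treatment, so a few discontinuers might still be scanned.
- *That the counted set alone makes the table wrong.* Binomial(15, p) holds under either count once p is defined.
- *That the same data are shown to close a group under one document and keep it open under the other.* The case in Step 4 shows a difference in timing. Opposite decisions are possible but not demonstrated.

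The objection does not remove the conflict. The triggers differ, no change is declared, and neither text limits the count to 15. The allocation plan makes 15 per group likely but does not guarantee it: the documents describe no enrollment pause at 15.

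**Conclusion.** The point holds as an undeclared conflict over who makes up the 15, together with a success count not tied to those 15 and a table column whose rate is undefined. The size depends on an assumed discontinuation rate. At 10% to 20% before Week 12, with 40% success among scanned participants and the Protocol's cut-off, counting discontinuers gives a stopping probability of 15.3% to 24.2%, where a reader taking the column as the rate among scanned subjects would expect 9.1%. The n = 20 figure illustrates sensitivity to the group size at the look; the documents do not predict that size.

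The difference in cut-off at the same place is separate. It is what makes SAP Table 8 numerically wrong for the SAP's own rule, so relabelling the column would not be enough. SAP Section 10.2.3 states that enrollment ended early, which limits the practical effect. Section 9 nevertheless still describes the look as planned, and any report of it needs one defined count. The correction should be made.

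**What to change.** Put one rule in the Synopsis, Protocol Section 9.5.2 and SAP Section 9: the look uses the first 15 participants enrolled in each group, and anyone among them without a Week 12 spleen volume, discontinuers included, counts as not stable or reduced. This agrees with the worst-rank treatment in the primary analysis.

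Relabel the left column of Protocol Table 16 and SAP Table 8 as the probability that a counted participant has an observed Week 12 change of 0% or less.

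In the same edit, reconcile the Protocol's fewer than 4 with the SAP's 4 or fewer, and print the probabilities that belong to the agreed cut-off. Record the clarification in SAP Section 10.1.

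The cost is a few sentences and, depending on the cut-off agreed, a recalculated table. The downside is that, for a given success rate among scanned participants, the chance of stopping is higher than under the Protocol's literal wording.

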## LIST OF ABBREVIATIONS

The following abbreviations and special terms are used in this clinical study Protocol.

Abbreviation	Definition
AE	adverse event
AKT	protein kinase B
ALT	alanine aminotransferase
ANC	absolute neutrophil count
AST	aspartate aminotransferase
BTK	Bruton's tyrosine kinase
CALR	calreticulin
CFR	Code of Federal Regulations
CI	clinical improvement
CMR	complete metabolic response
CMV	cytomegalovirus
CR	complete response
CRF	case report form
CT	computed tomography
CTCAE	Common Terminology Criteria for Adverse Events
CYP	cytochrome P450
DIPSS	Dynamic International Prognostic Scoring System
DLBCL	diffuse large B-cell lymphoma
DLT	dose-limiting toxicity
DNA	deoxyribonucleic acid
ECG	electrocardiogram
ECOG	Eastern Cooperative Oncology Group
EMH	extramedullary hematopoiesis
EOS	end of study
EOT	end of treatment
ET	essential thrombocythemia
FDA	Food and Drug Administration
FSH	follicle-stimulating hormone
GCP	Good Clinical Practice
HBV	hepatitis B virus
HCV	hepatitis C virus
HDL	high-density lipoprotein
HIPAA	Health Insurance Portability and Accountability Act of 1996

Abbreviation	Definition
HIV	human immunodeficiency virus
IB	Investigator's Brochure
ICF	informed consent form
ICH	International Conference on Harmonisation
IEC	independent ethics committee
IL	interleukin
IN	Investigator Notification
INR	international normalized ratio
irAE	immune-related adverse event
IRB	institutional review board
ITT	intent-to-treat
IXRS	interactive voice/web response system (use appropriate option and change to IVRS or IWRS throughout document)
IWG	International Working Group
JAK	Janus kinase
LDL	low-density lipoprotein
LCM	left costal margin
MedDRA	Medical Dictionary for Regulatory Activities
MF	myelofibrosis
MFSAF	Myelofibrosis Symptom Assessment Form
MPN-SAF	Myeloproliferative Neoplasms Symptom Assessment Form
MPN-SAF TSS	Myeloproliferative Neoplasm Symptom Assessment Form Total Symptom Score
MRI	magnetic resonance imaging
MRT	Myeloproliferative Neoplasms Research and Treatment
MTD	maximum tolerated dose
NHL	non-Hodgkin lymphoma
PD	pharmacodynamic
PET-MF	post-essential thrombocythemia myelofibrosis
PGIC	Patient Global Impression of Change
P-gp	P-glycoprotein
PI3K	phosphatidylinositol 3-kinase
PJP	Pneumocystis jirovecii pneumonia
PK	pharmacokinetic
PMF	primary myelofibrosis
PPV-MF	post-polycythemia vera myelofibrosis
PR	partial response
PRBC	packed red blood cell

Abbreviation	Definition
PT	prothrombin time
PTT	partial thromboplastin time
PV	polycythemia vera
Q3W	every 3 weeks
Q4W	every 4 weeks
Q12W	every 12 weeks
Q24W	every 24 weeks
QD	once daily
QW	once weekly
RBC	red blood cell
R-ICE	rituximab, ifosfamide, carboplatin, and etoposide
RNA	ribonucleic acid
SAE	serious adverse event
SAP	Statistical Analysis Plan
STAT	signal transduction and activator of transduction
TEAE	treatment-emergent adverse event
TG5	Treatment Group 5 mg (20 mg once daily × 8 weeks followed by 5 mg once daily)
TG5D	Treatment Group 5 mg daily from Day 1 to end of treatment
TG5I/M	Treatment Group 20 mg once daily × 8 weeks followed by 5 mg once daily until end of treatment . Note this Part 4 dose group is identical to TG5 in Part 3.
TG10	Treatment Group 10 mg (10 mg once daily × 8 weeks followed by 10 mg once weekly)
TG20	Treatment Group 20 mg (20 mg once daily × 8 weeks followed by 20 mg once weekly)
TEN	toxic epidermal necrolysis
[REDACTED]	[REDACTED]
ULN	upper limit of laboratory normal
UNL	upper normal limit
WBC	white blood cell

## 1. INTRODUCTION

INCB050465 represents a novel, potent, and selective inhibitor of the Class IA phosphatidylinositol 3-kinase (PI3K) enzymes, with selectivity for the  $\delta$  isoform, which is proposed for development for treatment of hematological malignancies. For a thorough discussion of the pharmacology of INCB054065, refer to the INCB054065 Investigator's Brochure ([IB](#)). Ruxolitinib, a potent and selective inhibitor of the Janus kinase (JAK) family of protein tyrosine kinases, JAK1 and JAK2, is approved in multiple jurisdictions for myelofibrosis (MF), with variations on the specific indication language, and is currently in development for the treatment of myeloproliferative neoplasms, hematologic malignancies, and solid tumors. For a thorough discussion of the pharmacology of ruxolitinib (INCB018424), refer to the [ruxolitinib IB](#).

### 1.1. Overview of Myelofibrosis

The classic myeloproliferative neoplasms (MPNs) include chronic myelogenous leukemia, polycythemia vera (PV), essential thrombocythemia (ET), and primary myelofibrosis (PMF). Myelofibrosis can present as a *de novo* disorder (PMF) or evolve secondarily from previous PV or ET (post-polycythemia vera myelofibrosis [PPV-MF] or post-essential thrombocythemia myelofibrosis [PET-MF]). Regardless of whether MF is a primary or secondary disorder, it is characterized by a clonal stem cell proliferation associated with production of elevated serum levels of multiple inflammatory and proangiogenic cytokines, a characteristic bone marrow stromal pattern that includes varying degrees of collagen fibrosis, osteosclerosis and angiogenesis, and a peripheral blood smear showing a leukoerythroblastic pattern with varying degrees of circulating progenitor cells. Clinically, MF is characterized by progressive anemia, leukopenia or leukocytosis, thrombocytopenia or thrombocythemia, and multiorgan extramedullary hematopoiesis most prominently involving the liver and spleen. Patients may experience debilitating symptoms ([Mesa et al 2013a](#), [Mesa et al 2013b](#)), sequelae of massive splenomegaly (pain, limitations of movement, early satiety and shortness of breath, hepatic obstruction, and splenic infarction), a hypermetabolic state with cachexia, progressive hematopoietic failure, progression to leukemia, and premature death.

The median age at diagnosis of MF is approximately 60 to 65 years, and the incidence of PMF has been estimated at 4 to 6 cases per 100,000 people in the US ([Stein et al 2015](#)). Survival in MF varies with the presence or absence of specific risk factors. Analysis of risk factors over the last 20 years has resulted in a number of prognostic scoring systems (for a review, refer to [Bose and Verstovsek 2015](#)). A prognostic scoring system based on a time-dependent risk evaluation has been developed: the Dynamic International Prognostic Scoring System (DIPSS) for PMF ([Passamonti et al 2010](#)). Age of greater than 65 years, presence of constitutional symptoms, anemia (hemoglobin less than 100 g/L), leukocytosis (white blood cell [WBC] count  $> 25 \times 10^9/L$ ), and a circulating blast percentage of 1% or higher were assessed for their impact on survival when analyzed as time-dependent covariates in a multivariate Cox proportional hazard model. The approach showed that acquisition of anemia over time affects survival with a hazard ratio roughly double that of other parameters, and therefore anemia was assigned a score of 2, while the other 4 factors were assigned scores of 1. Four risk categories with nonoverlapping survival curves have been described in [Table 1](#).

